## 5.0 Procedures Involved

# 5.1 Study Design

The research design includes both a Community-Based Participatory Research design in the initial phases to adapt the existing program for use in a rural community as well as a Randomized Controlled Trial (RCT) to test the modified program with 120 7-10 year old children and the primary meal preparer in the family. In the RCT, 60 families will be randomized to receive the NU-HOME program while the other 60 families will receive a delayed program after they have completed data collection.

### **5.2 Study Procedures**

During the initial planning stage, Action Team members will meet monthly and use CBPR principles to adapt the existing program for use with rural families. During committee meetings, community assets will be mapped to facilitate buy-in and ensure inclusion of necessary partners, and assess and finalize our strategies. A logic model of the relationships between program resources, activities, outputs and outcomes will be created using a graphical depiction to address needs of the rural communities and facilitate implementation and uptake. An ongoing evaluation of the extent to which CBPR principles are followed will be conducted through CBPR surveys. (Change in protocol to submit survey items and Action Team Consent Form was approved 10/12/16.)

During the RCT, 120 7-10 year-old children and their primary meal-preparing parent/guardian will complete measurements at three time points: baseline (before randomization), at post intervention (8-10 months after randomization) and at follow-up (14-16 months post randomization). At the baseline visit, adult participants will provide written consent for participation and children will provide written assent. Trained study-staff will measure the height and weight of the adult and child participants. Online surveys will be

VERSION DATE: 4/22/19

completed on an electronic device (laptop, ipad, phone) by the adult participant to assess household level data (e.g., home food availability, family meal frequency and environment, nutritional quality of foods served at meals and snacks) and individual-level data (physical activity, usual fruit and vegetables intake). The parent and child will also participate in two interviews about the food the child had to eat in the past 24-hours. (Change in protocol for child interview to parent and child interview and from three to two interviews approved 4/24/17.) The child will also wear an accelerometer to assess their physical activity. The child participant will also complete surveys to assess individual level data (e.g., fruit and vegetable preferences).

### 5.3 Follow-Up

Data will be collected at post intervention (8-10 months post randomization) and at Followup (14-16 months post randomization)

## 5.4 Individually Identifiable Health Information

In our initial application, we completed appendix H and were awarded a waiver of HIPAA authorization requirement. As part of our recruitment strategy, we proposed using personal health records available to a study Co-Investigator ([name], a community partner from Allina Health who was awarded a subcontract) to identify potentially eligible participants for a recruitment mailing. The UMN academic researchers on the team will not have access to PHI. [name] will access medical records at the New Ulm Medical Center to identify parent names and addresses of children who are eligible to participate in the NU-HOME study (i.e., they will be 7-10 years old). This information will only be used to send an introduction letter (from Allina Health) about the study and invite the parent to participate. [name] will not send PHI to the UMN researchers and it will not be retained as research data. As enrollment begins, [name] will compare names of enrolled parents to her list of those included in the mailing so we can assess the effectiveness of this recruitment method; she will only share the aggregate information.

As part of the research, the NU-HOME team will be collecting personal identifiable information including full names, birthdays, telephone numbers, email addresses, and mailing addresses of enrolled participants. Direct identifiers will be maintained so we can contact participants (by mail, email, or telephone) to schedule their data collection visits, inform them of their randomization status, remind them of intervention session dates and conduct goal-setting phone calls. We will contact families to inform them if they are in the intervention or the delayed intervention group. We will also ask both child and adult participants a separate question on the consent form asking for permission to take their photographs. Photos will be taken at intervention sessions to share with families and in presentations but will not be used as data. Participants are free to say YES or NO to the item on photographs while continuing to participate in other research activities with the study. In all cases, the privacy of measurements for each child and parent will be maintained, and all measurements will be carried out in a sensitive, nonjudgmental and positive atmosphere.

### 6.0 Data Banking

### 6.1 Storage and Access

Participating families will be assigned a unique study ID number. The ID number will be linked to the identifying information and stored on a secure REDcap server accessible only by study staff with approved access. Participant height and weight and the Home Food Inventory data are collected on paper and entered into a secure REDCap server. The hard copies are deidentified and are stored in a locked file cabinet in the School of Nursing. All

VERSION DATE: 4/22/19

other data are collected via an online REDCap survey and stored on a secure REDCap server. Data are downloaded on a regular basis and saved to Box in a folder that is only accessible to the Principal Investigator and Project Manager. When the data have been cleaned and prepared for analysis, deidentified datasets are uploaded to a folder that is shared with the analyst at Allina Health.

#### 6.2 Data

Deidentified data that may be used for future use include all survey data, dietary recall data, physical activity data, height and weight data and all process data related to intervention attendance and participation. In addition, identifiable data such as name, address, phone number and email which we used to contact participants and will be maintained for seven years after the end of the study.

## 6.3 Release/Sharing

After data entry, cleaning and linkage, a de-identified data set will be created which, along with associated documentation, will be made available to users after analyses related to the major aims of the study have been reported and only under a data-sharing agreement as suggested by the NIH that provides for: (1) a commitment to using the data only for research purposes and not to identify any individual participant; (2) a commitment to securing the data using appropriate computer technology; and (3) a commitment to destroying or returning the data after analyses are completed. Any request for data will be evaluated by the study Principal Investigator.

# 7.0 Sharing of Results with Participants

#### 7.1 Describe Whether Results Will Be Shared and How

As part of the CBPR work with the Action Team in stage 4 (Year 5), decisions will be made as a group about when to share data with participants and the community, what data to share and how the data will be shared. Expected venues for sharing study results will include traditional academic journals, research conferences, technical and lay reports (to parents, health care professionals, and stakeholders), local non-research conferences at schools, community events, and media. The Research Team has experience writing about main study findings in lay reports and disseminating to participants.

### 8.0 Study Duration

### 8.1 Describe

Action Team members will be involved in all five years of the study. In the first year of the study, they will work to adapt the existing HOME Plus program for rural families and later will work to solidify plans for the delayed intervention and be involved in deciding how to disseminate study findings. Mail trial participants will be involved in the study for approximately 1.5 years from baseline data collection through follow-up data collection. The study is funded for five years and includes planning, implementation of the RCT, a delayed intervention and dissemination of findings.

### 9.0 Study Population

#### 9.1 Inclusion Criteria

Child participants must be between 7 and 10 years old and live with the adult participant at least 50% of the time. The adult participants must be the primary-meal preparing parent/guardian.

#### 9.2 Exclusion Criteria

VERSION DATE: 4/22/19

Participants must not be planning on moving away from the area in the next year and be free from medical conditions contraindicating study participation.

## 9.3 Screening

For Cohort 1, interested individuals will call the Evaluation Director to be screened for eligibility. She will describe the study, answer any questions, and ask additional questions to determine eligibility based on inclusion and exclusion criteria. For Cohort 2, attempts are being made to increase the diversity of the study sample. Flyers will be distributed in both English and Spanish. The flyers in Spanish will direct interested families to a bilingual staff member who will screen them for eligibility. For Cohort 2, study staff will also be available at community events to screen interested families in person. Families will be offered small trinkets to increase interest in learning about the research study. Trinkets will be of minimal monetary value (\$1.00 or less) and will include items such as fruit and vegetable stress balls, pens, note pads, jump ropes and indoor Frisbees.

# 10.0 Vulnerable Populations

### 10.1 Identify

Child between the ages of 7-10 years are included in the study. One parent is required to provide consent for their participation and the children are required to provide assent to enroll.

Pregnant women may be included as being pregnant is not an exclusion criterion. Healthful eating would benefit a pregnant woman and neither the intervention or the measurement pose more than minimal risk to the pregnant woman or her fetus.

### 10.2 Adults Lacking Capacity to Consent

N/A

## 10.3 Additional Safeguards

See 10.1

## 11.0 Number of Participants

# 11.1 Number of Participants to be Consented

For the CBPR planning phase, we anticipate approximately 15 community members will be consented as members of the Action Team. (Change in protocol to add an Action Team Consent Form was approved 10/12/16.)

For the main trial, 120 parent/child dyads will be enrolled (total = 240 individuals).

### 12.0 Recruitment Methods

#### 12.1 Recruitment Process

Recruitment will be conducted by UMN staff and community partners, including area schools, Allina Health, New Ulm Medical Center physicians, UMN Extension Service, Brown County Public Health and community organizations. We will use direct mailing, flyers, presentations and other public announcement delivery channels. Current study participants will also be contacted and asked to share approved study flyers with any friends who they think might be interested in the study. All recruitment materials will direct interested families to contact the Evaluation Director by phone for eligibility screening (or a bilingual staff member for families calling from the Spanish flyer). Stud staff will also be available to screen interested families in person at community events and families will be offered small trinkets to increase interest in learning about the research study. Trinkets will

VERSION DATE: 4/22/19

be of minimal monetary value (\$1.00 or less) and will include items such as fruit and vegetable stress balls, pens, note pads, jump ropes and indoor Frisbees.

## 12.2 Sources of Participants

We will use community recruitment so participants will be any members of the New Ulm and surrounding communities who meet eligibility requirements. In addition, [name], the Allina Health Co-Investigator, will identify eligible children (based on age) in the New Ulm Medical Center records and send their family a letter of invitation.

#### 12.3 Identification of Potential Participants

In some cases, individuals will self-identify as a possible participant based on flyers in the community. In others cases, we will target potentially eligible families. For example, we will send flyers home from school with students in grades that correspond to the 7-10 year old age range. In addition, [name], the Allina Health Co-Investigator, will identify eligible children (based on age) in the New Ulm Medical Center records and send their family a letter of invitation. [name] will make initial contact with potential subjects within this method of recruitment. The PI and other UMN researchers will not have access to the medical records. Interested families will be directed to call the Evaluation Director for eligibility screening (or a bilingual staff member for families calling from the Spanish flyer). Current study participants will also be contacted and asked to share approved study flyers with any friends who they think might be interested in the study.

#### 12.4 Recruitment Materials

We will use direct mailing, flyers, presentations and other public announcement delivery channels. Current study participants will also be contacted and asked to share approved study flyers with any friends who they think might be interested in the study. (Change in protocol in which we submitted final recruitment materials was approved 3/27/17.) (Change in protocol submitted 3/20/2018 for recruitment materials for Cohort 2 with names of both major towns included in Cohort 2 as well as a Spanish version of the flyer). Families will be offered small trinkets to increase interest in learning about the research study. Trinkets will be of minimal monetary value (\$1.00 or less) and will include items such as fruit and vegetable stress balls, pens, note pads, jump ropes and indoor Frisbees.

#### 12.5 Payment

At each data collection visit, families will receive a \$25 gift card for height and weight measurement and for completing surveys that day. Over the following two weeks, they will receive an additional \$25 gift card for completing one additional phone interview about the food the child ate the previous day and returning the physical activity tracker the child wore for 7 days. The family will receive a third \$25 gift card for completing the snack and evening meal screener surveys. Thus, if a family completes all of the planned data collection at each data collection period, they will receive \$75 each time (total of \$225 in gift cards per family if they complete all data collection at each of the 3 data collection time points). (Change in protocol to break up the \$75 payment into three separate \$25 allotments was approved 4/26/17.) Cohort 2 families who complete the interim child height and weight measurement will receive a \$15 gift card. At post-intervention data collection, Cohort 2 families who wear their actigraph long enough will be entered to win a pack of 10 passes to the Sleepy Eye waterpark. On each day a child participant wears their actigraph for at least 12 hours, their name will be entered into the drawing. The drawing will take place this summer. Families will not receive direct compensation for attendance at intervention sessions (primary or delayed intervention); however, as attendance at each session is logged, participating families will receive a \$10 gift card to compensate them for gas while

VERSION DATE: 4/22/19

attending intervention sessions since this study is being conducted in a rural area and participants may drive quite far to participate. In addition, at each in-person session, families may receive take-home groceries of the featured monthly fruit/vegetable. Families may also add their names for drawings for door prizes (e.g., kitchen equipment, pass to local physical activity facility) and a chance to win the opportunity to have a home visit by a chef. Participants will be notified that this is a drawing and not everyone will receive this incentive.

## 13.0 Withdrawal of Participants

## 13.1 Withdrawal Circumstances

We do not anticipate situations where a participant would be withdrawn without their consent.

#### 13.2 Withdrawal Procedures

#### 13.3 Termination Procedures

As we do not anticipate terminating participants, if this situation arises, we will submit a change in protocol and receive approval before doing so.

# 14.0 Risk to Participants

## 14.1 Foreseeable Risks

The study has minimal risks. Participants may feel uncomfortable answering questions about their own or their family's eating habits but they are told they can skip any survey questions they do not wish to answer. Participants may also feel uncomfortable completing measurements as part of data collection in a group setting; however, we provide partitions for privacy when measuring height and weight, do not indicate their height or weight verbally and provide separate tables between families for completion of surveys. Participants may have some conflict about changing the food offerings or television limits in their home; however, families will choose from several behavioral goals provided.

# 14.2 Reproduction Risks

N/A

#### 14.3 Risks to Others

N/A

### 15.0 Incomplete Discloser or Deception

### 15.1 Incomplete Disclosure or Deception

N/A

## 16.0 Potential Benefits to Participants

#### 16.1 Potential Benefits

There are no direct benefits to participation; however participants are taught to make healthful food choices and may improve their health if they make dietary changes or improve the heathfulness of the foods in their home food environment.

#### 17.0 Data Management

#### 17.1 Data Analysis Plan

Analysis plan. The analysis plan integrates our theoretical framework for behavior change and our temporal design. The analysis plan includes descriptive analyses, assessment of

VERSION DATE: 4/22/19

primary and secondary outcomes, and testing of potential moderation and mediation effects using an intent-to-treat methodology.

Descriptive analyses. Baseline participant characteristics will be reported using means and standard deviations or median for continuous measures and frequencies for categorical measures. To examine group comparability at baseline, differences between intervention and wait-list controls will be assessed using chi-square tests for categorical data or two-sample t-tests for comparisons of continuous data. Descriptive statistics of all outcome measures will be calculated at each assessment period. Inter-item correlations and internal consistency measures (i.e., Cronbach's alpha) will also be calculated.

Primary outcome analyses. For the analysis of the primary outcome of child BMI, a two-step approach will be used. First, two-sample t-tests will be used to assess potential changes in age- and gender-adjusted child BMI z-scores from baseline to post-intervention (i.e., immediate change). Second, baseline-adjusted analysis of covariance while adjusting for child age, gender, race and economic assistance will be performed. Analyses of associations with overweight status will be conducted with multivariate logistic regression while adjusting for baseline BMI z-scores or BMI z-squared to allow for curvature. Sustained program effects will be assessed using a similar approach with follow-up BMI z-scores.

Intent-to-treat principle. All comparisons will be performed under the intent-to-treat principle (i.e., all randomized participants will be included and analyzed according to group assignment, regardless of compliance). A 5% two-sided type I error rate will be used to determine statistical significance. SAS software version 9.4 (SAS Institute Inc., Cary, NC, USA) will be used for statistical analyses. Because the intervention is delivered in multiple family groups, we anticipate group facilitation effects (i.e., participants have greater benefits than if the intervention were delivered individually). Thus, we will investigate intraclass correlations (ICCs) in the test for intervention effectiveness.

Secondary outcome analyses. Secondary outcomes will be analyzed using the same approach as with the primary outcome. In addition, to compare study groups over time, linear mixed models with baseline measures, group, and time (baseline, post-intervention and follow-up) as fixed covariates will be fitted. Group by time interactions will also be introduced. Transformation will be considered to ensure data normality. Other potential covariates (i.e., gender, age, education level, rural code) will be entered in models, if necessary. These models will assess between-group effects following randomization, within-group changes, and whether changes in the outcomes from baseline to post-intervention or to follow-up differed between the groups (group x time interaction). Based on preliminary studies, we expect that intervention families will have changes in food availability and intake, physical activity and sedentary behaviors after receipt of the NU-HOME program that will remain consistent at follow-up.

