#### 17.2 Power Analysis

Power calculations are based on two assessment time points, correlation over time, and variability of age- and gender-adjusted BMI z-scores. We propose to recruit 120 families (one eligible child and one parent per family) to allow for a 15% attrition rate with a final effective sample of about 100 families in the study by the end of follow-up. Using child (<11 years old) data from the HOME Plus trial, we estimated a within-child correlation (p) between the primary outcome measurements over time of 0.9. Utilizing a baseline-adjusted analysis approach, with a sample size of 96 (48 per group), we will be able to detect an

VERSION DATE: 4/22/19

effect size (ES) of 0.25 for age- and gender-adjusted BMI z-scores at 80% power. This effect size corresponds to approximately 1.4 kg decrease in average weight gain between intervention and control groups. This corresponding decrease was estimated using BMIi=M(1+LSzi)1/L formula with age-and gender-specific L,M,S parameters and average weight and height values for 8-10 year old boys and girls [at 50th or higher percentile for weight].

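### The added mixed model for secondary outcomes uses baseline both as a covariate and as a time level, and ties the post-randomisation group effect to no coefficient

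*Combined protocol and SAP*

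**What the plan says.** Section 17.1 (Secondary outcome analyses) starts from the primary-outcome methods: "Secondary outcomes will be analyzed using the same approach as with the primary outcome". Those are a t-test on change, then baseline-adjusted ANCOVA. In addition, "linear mixed models with baseline measures, group, and time (baseline, post-intervention and follow-up) as fixed covariates will be fitted". It continues: "Group by time interactions will also be introduced".

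Three targets follow. Two are given as "These models will assess between-group effects following randomization, within-group changes". The third is "whether changes in the outcomes from baseline to post-intervention or to follow-up differed between the groups (group x time interaction"; only this one is tied to a model term.

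The baseline-measures term is not defined. Demographic variables come in a separate sentence, "Other potential covariates (i.e., gender, age, education level, rural code) will be entered in models, if necessary", so the outcome's own baseline value is the most natural reading. The section does not say that the baseline row is dropped from the outcome vector, that the arms share a baseline mean, which of the two fits is reported, or what covariance structure is used. The significance rule is "A 5% two-sided type I error rate will be used to determine statistical significance".

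**The concern.** Baseline can enter a longitudinal model as a covariate or as an outcome row. Using it as both causes two separate problems.

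- **Dilution.** A single group coefficient over three visits averages in a visit before randomisation, where the true effect is zero. This comes from the time level alone, with or without the covariate.
- **Wrong standard error.** With the covariate in the model, the baseline row is partly predicted by itself. Its residual is artificially small and pulls down the variance that a random-intercept model applies to all visits. A group contrast at one later visit then looks more precise than it is.

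An analyst who follows the plan must choose a coefficient for the post-randomisation group effect, perhaps after seeing results. The candidates give about two thirds of the effect, about zero, or the full effect from the same data. A diluted estimate would also disagree with the ANCOVA estimate in the same report.

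**Working it through.** **Inputs.** From section 17.2: 48 per group, effect size 0.25, 80% power and correlation 0.9 (all for BMI z-score), and 15% attrition. From section 17.1: two-sided 5%. Assumed, because the documents give nothing for secondary outcomes: SD 1, equal correlation rho of 0.3, 0.5 or 0.7 between visits, and the same effect d at both later visits.

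**The plan's own figure.** For ANCOVA, n per group = 2(1.96 + 0.8416)²(1 − 0.9²)/0.25² = 2 × 7.849 × 0.19/0.0625 = 47.7, so 48. The stated 96 reproduces. It concerns the primary outcome; no figure is given for the mixed model.

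**Pooled group term (no interaction).** With complete data it estimates (0 + d + d)/3 = 2d/3, so 0.33 for d = 0.50. Adjusting a child's three-visit mean for baseline leaves exactly two thirds of the adjusted mean of the two later visits. Estimate and standard error therefore shrink together, and the test hardly moves. At rho 0.5 the standard errors are √[(2/48)(0.6667 − 0.4444)] = 0.096 (pooled) and √[(2/48)(0.75 − 0.25)] = 0.144 (later visits only), a ratio of 2/3.

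The interval is centred d/3 too low. At rho 0.5 and d = 0.50 the bias is 0.167/0.096 = 1.73 standard errors, which gives coverage of about 59%. Simulation with random-intercept REML, 4,000 or more data sets per setting:

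| Pooled term | Mean | 95% interval coverage at rho 0.3, 0.5, 0.7 |
|---|---|---|
| d = 0.50, complete, 48 per arm | 0.33 | 65%, 60%, 48% |
| d = 0.50, attrition, 60 per arm | 0.32 | 53%, 46%, 31% |
| d = 0.25, complete | 0.17 | 87.6%, 87.0%, 82.6% |
| d = 0.25, attrition | 0.16 | 85.7%, 82.5%, 76.5% |

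Attrition is 15% by follow-up, assumed missing at random and half of it by post-intervention. That leaves 60, 55.5 and 51 per arm, and later visits make up 106.5/166.5 = 0.64 of the rows. Without the covariate and with d = 0.50 the mean is 0.33 to 0.34 (complete) and 0.31 (attrition), so the covariate is not the cause. Rejection rates differ from a test on later visits only by at most 1.2 points.

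**Visit-specific group contrast (group plus interaction).** The fitted baseline slope is (1 + 2rho)/3, which is 2/3 at rho 0.5. Residual variance is (1 − 2/3)² = 0.111 at baseline and 1 − 2(2/3)(0.5) + (2/3)² = 0.778 at each later visit. The model applies the average, (0.111 + 2 × 0.778)/3 = 0.556. The reported standard error is then √(0.556 × 2/48) = 0.152, against a true √(0.778 × 2/48) = 0.180. The nominal 5% test rejects at |z| > 1.96 × √(0.556/0.778) = 1.66, a rate of 9.8%. The same formula gives 9.1% at rho 0.3 and 10.3% at rho 0.7.

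| Type I error at rho 0.3, 0.5, 0.7 | Result |
|---|---|
| Visit contrast, complete data | 8.5%, 9.9%, 10.2% |
| Visit contrast, attrition | 9.6%, 10.4%, 10.7% |
| Visit contrast without the covariate | 4.6% to 5.5% |

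Repeat complete-data simulations (1,500 to 2,500 data sets per setting) gave 8.3% to 11.2% with the covariate. The double use is the cause.

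**Unstructured covariance.** Slope 1 on the covariate, with zero intercept and group effect at baseline, fits the baseline row perfectly, so the REML likelihood has no maximum. Each 100-fold fall in the baseline residual variance raises the log-likelihood by about (96 − 3)/2 × ln 100 = 214. One simulated data set showed −319, −105, 109, 323 and 537 for variances 1, 10⁻², 10⁻⁴, 10⁻⁶ and 10⁻⁸.

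**Group-by-time contrast.** Mean 0.50 for a true 0.50, with type I error of 4.4% to 5.7%. The covariate does not alter it; it is a change-score contrast. Its variance relative to ANCOVA is 2(1 − rho)/(1 − rho²) = 2/(1 + rho), that is 1.54, 1.33 and 1.18. At rho 0.5 and d = 0.50, simulated power is 68% against 80% for ANCOVA.

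**The case against.** The strongest reply is that the interaction model carries the inference. The plan names the group-by-time term, that term is sound, and a coefficient that averages in a pre-randomisation visit is not an effect after randomisation. Each later visit also already has a valid ANCOVA estimate. The inflated error rate needs several things at once: the undefined term must mean the outcome's own baseline, the baseline row must stay in, the covariance must be a random intercept or compound symmetry, and a visit-specific contrast must be reported. The worst coverage figures use an assumed 0.50 SD, twice the only effect size in the plan.

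Most of this stands and sets the severity. It does not remove the point. The plan lists the post-randomisation group effect apart from the interaction, so something other than the interaction may be reported for it. If the baseline term meant only other characteristics, the standard-error problem would go, but the dilution and the unassigned target would remain. At 0.25 SD with complete data the pooled interval still covers only 83% to 88%. An unbounded likelihood would probably show up as a failed fit, so it is less likely to mislead silently.

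**Conclusion.** The specification is wrong as written, but the consequence is minor. The harm depends on a choice the plan leaves open:

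- **Pooled group term reported:** the estimate is about one third too small, while significance decisions hardly change.
- **Visit-specific contrast under a random intercept:** the false-positive rate is about 9% to 11% instead of 5%, if the covariate is the outcome's own baseline.
- **Only the group-by-time contrast reported:** neither problem arises, at some loss of precision relative to ANCOVA.

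The sizes rest on assumed correlations of 0.3 to 0.7, equal effects at both later visits and, for the attrition figures, data missing at random. The primary analysis, the sample size and the secondary t-tests and ANCOVA are not affected.

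**What to change.** Use baseline once, in either of two ways.

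1. Keep baseline as an outcome row, drop it as a covariate, and constrain the arms to a common baseline mean: time, plus group-by-time terms at the two later visits only.
2. Keep the baseline covariate and use only post-intervention and follow-up as outcome rows, with group, time, group-by-time and baseline-by-time.

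In simulation both gave a mean of 0.50 for a true 0.50, coverage of 94% to 96% and type I error of 4.5% to 5.4%.

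In either case, define the baseline-measures term, name the group contrast at each post-baseline visit as the between-group effect, and state the covariance structure. The cost is two or three sentences in section 17.1 and no extra data. With the second option, within-group change from baseline has to be reported separately.
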